9.9. Concomitant Medication

Data on Concomitant Medication will be collected at the baseline and at each 3 monthly follow-up visit and will contribute to the Health Economics analysis. There are no restrictions on what medication can be used. All chemotherapy should be recorded as standard.

10. Decision Points

10.1. D1

The diagnosis, stage and management plan from the MDT meeting will be recorded in the CRF as D1 at this point. D1 is the decision made by the clinicians UNBLINDED using the usual diagnosis strategy based on the multidetector CT and MDT meeting outcome and following local practices. The decisions will be categorised according to diagnosis, staging and management.

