10.1.3. Management

Management will be categorised according to one or more of the following options:

1. Resection (+/-prior laparoscopy)
2. Biopsy (EUS/percutaneous)
3. Drainage procedure, e.g. stent or surgical bypass
4. Chemotherapy/trial
5. Best supportive care
6. Clinical follow up +/- further investigation
7. No further management required
8. Other

10.2. D2

After the additional PET/CT scan has been performed the diagnosis, stage and management plan will be re-evaluated by the investigator or at another MDT meeting and will be recorded in the CRF as D2 at that point. Categories will remain the same as D1.

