10.5.1. Reference Standards

The reference standard for diagnosis will be a clinical judgement made by an independent panel based on histology (either biopsy or resection) or clinical outcome at the 12 month assessment. Estimated patient numbers for biopsy are 150, resection 300 and follow up 150. The panel will agree on the appropriate staging for each patient with pancreatic cancer and appropriate management – to be used as reference diagnoses D4.

10.5.2. Stage 1

The panel will initially receive a patient histology report for the target conditions:

- Pancreatic cancer (for the primary objective)
- Stage of pancreatic cancer (UICC TNM 7th Edition, 2009, classification as above for resectable, borderline resectable and unresectable disease)
- Chronic pancreatitis
- Particular types of pancreatic tumour.

In addition to this they will be provided with information about the clinical status of the patient at 12 months (but excluding all information from investigations made at baseline and the PET/CT test results). This will be according to the minimum dataset of the Royal College of pathologists [47], in a standard format for resection histology, this will include pathological staging (pTNM) for tumours.

10.5.3. Stage 2

If the panel is unable to make a firm reference diagnosis based on the above information, results of baseline investigations will be released but not the PET/CT investigation.

The two stage process is planned so that the panel's initial decision is not contaminated by the standard work up of either set of test results, and never by the PET/CT scans results and avoids incorporation bias. Finally the panel will also be asked to judge the appropriateness of management for each patient and if a change prompted by PET/CT was appropriate.

11. NCRI PET Core lab

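### At Stage 2 the reference panel sees the tests behind D1 but not PET/CT, so the unqualified claim to avoid incorporation bias is wrong for those patients

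*Protocol*

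**What the plan says.** Section 10.1 defines D1 as the decision made "UNBLINDED using the usual diagnosis strategy based on the multidetector CT and MDT meeting outcome". Section 10.2 defines D2 as follows: "After the additional PET/CT scan has been performed the diagnosis, stage and management plan will be re-evaluated by the investigator or at another MDT meeting". D2 therefore rests on the baseline information plus PET/CT.

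Section 10.5 builds the reference D4 in two steps. At Stage 1 (section 10.5.2) the panel receives the histology report and the 12-month clinical status, "excluding all information from investigations made at baseline and the PET/CT test results". Stage 2 (section 10.5.3) applies in this case: "If the panel is unable to make a firm reference diagnosis based on the above information". Then "results of baseline investigations will be released but not the PET/CT investigation".

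The justification in section 10.5.3 has two parts. Freedom from the standard work-up is stated for the panel's initial decision only. The second part carries no such limit: "never by the PET/CT scans results and avoids incorporation bias".

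Section 12.4 scores D1 and D2 against D4 as sensitivities and specificities and tests the within-patient change with McNemar's test.

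**The concern.** Incorporation bias arises when a test under comparison helps to form the reference it is judged against. The trial compares two diagnostic strategies, standard work-up (D1) and standard work-up plus PET/CT (D2). Keeping PET/CT away from the panel protects against one form of this bias. At Stage 2 the panel is given the ingredients of D1 and denied the only additional ingredient of D2, so the incorporation that remains is one-sided.

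Where D1 and D2 agree, both gain from it. Where they disagree, D4 is drawn towards D1. McNemar's test uses only the disagreements, so the primary comparison is affected in its informative patients. A reader who trusts the sentence in section 10.5.3 would not look for this. Unless the D4 form records which stage settled each case, nobody could check it afterwards.

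**Working it through.** **1. The plan's own figures.** Section 12.2 gives sensitivity 81% to 90%, specificity 66% to 80%, 80% power, 5% two-sided, and 87 to 281 diseased and 57 to 221 non-diseased. The paired relative-rate formula is

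n = [(1.960 + 0.842)/ln g]² × [(g + 1)p₁ − 2j] / (g p₁²), with g = p₂/p₁ and j the joint proportion.

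- Diseased (p₁ = 0.81, p₂ = 0.90): j = 0.81 gives 87.3; j = 0.71 gives 281.3.
- Non-diseased, false-positive rates (p₁ = 0.34, p₂ = 0.20): j = 0.20 gives 57.4; j = 0 gives 221.4.
- 281/0.47 = 598, rounded in the protocol to 600. Section 12.3 later sets 500.

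The stated sizes reproduce, so these inputs and ranges of j are a fair base. The protocol states no figure for an incorporation effect.

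**2. Model for Stage 2.** A share s of patients reaches Stage 2. In a fraction a of them D4 equals the D1 call; in all other patients D4 equals the truth. Put w = s × a. Both s and a are assumptions. Stage 2 membership is taken as unrelated to true status and to the test errors. Prevalence is 0.47. Middle correlation means that both calls are positive in 0.76 of the diseased and in 0.10 of the non-diseased.

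- P(D1+) = 0.47 × 0.81 + 0.53 × 0.34 = 0.5609, so P(D1−) = 0.4391
- P(both +) = 0.47 × 0.76 + 0.53 × 0.10 = 0.4102
- P(both −) = 0.47 × 0.05 + 0.53 × 0.56 = 0.3203

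**3. Worked case: s = 10%, a = 0.5, w = 0.05.**

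- Labelled diseased: 0.95 × 0.47 + 0.05 × 0.5609 = 0.4745
- Apparent sensitivity D1: (0.95 × 0.3807 + 0.05 × 0.5609)/0.4745 = 0.821
- Apparent sensitivity D2: (0.95 × 0.4230 + 0.05 × 0.4102)/0.4745 = 0.890
- Labelled non-diseased: 1 − 0.4745 = 0.5255
- Apparent specificity D1: (0.95 × 0.3498 + 0.05 × 0.4391)/0.5255 = 0.674
- Apparent specificity D2: (0.95 × 0.4240 + 0.05 × 0.3203)/0.5255 = 0.797

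The differences are 6.9 points (sensitivity) and 12.3 points (specificity), against 9 and 14.

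**4. Range of results, a = 0.5.** The power column is for the sensitivity difference with 500 patients at middle correlation.

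| Stage 2 share | Sensitivity gain, middle (range over correlation) | Specificity gain, middle (range) | Power |
|---|---|---|---|
| 0% | 9.0 | 14.0 | 0.89 |
| 5% | 7.9 (7.5–8.3) | 13.1 (12.8–13.5) | 0.80 |
| 10% | 6.9 (6.1–7.7) | 12.3 (11.6–13.0) | 0.67 |

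In every scenario tried with w above zero, D1's sensitivity and specificity rose and both differences shrank.

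**The case against.** The strongest reply is that the protocol is largely right. PET/CT is the test under evaluation and it is kept out of the reference. The text openly says that baseline results are released at Stage 2, and it claims freedom from the standard work-up only for the initial decision. All of that stands. The fault is the unlimited closing phrase and the lack of any provision for its consequence at Stage 2.

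Five stronger conclusions are tempting, and the documents do not support them.

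- **A 25% share and a reversed result.** A reader might take the 150 of 600 patients expected to have follow-up only (section 10.5.1) as the Stage 2 group. But 12-month status is Stage 1 evidence, so these patients are not Stage 2 by default. If the panel also copied D1 in all of them, the sensitivity gain would be −2.8 points with independent errors but +2.7 at maximum agreement. The reversal is a product of stacked assumptions, including a panel that sets aside the histology and outcome it already holds.
- **Staging as D1 against itself.** Section 10.5.1 says "The panel will agree on the appropriate staging for each patient with pancreatic cancer", and pathological stage is promised only for resections, so staging of unresected patients may well lean on baseline imaging. That remains an inference: the Stage 2 trigger names a firm diagnosis, not a firm stage, and 300 of 600 patients were expected to be resected.
- **A contradiction over PET/CT.** The panel must also judge "if a change prompted by PET/CT was appropriate". This task is placed last and can be read as following D4. What is missing is an explicit lock.
- **Stage 2 as the hard-to-diagnose group of section 4.5.** That group is difficult at presentation. Stage 2 patients are those still unresolved after histology and 12 months. The two need not coincide.
- **A trial biased overall against PET/CT.** Management informed by PET/CT helps to decide who obtains histology, and that could act the other way.

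A Stage 1-only sensitivity analysis may also sit in an analysis plan that is not shown. It could be run only if the stage of each D4 decision is recorded.

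**Conclusion.** The point holds for patients who reach Stage 2. The statement that the process avoids incorporation bias is correct for PET/CT and for Stage 1, and wrong as an unlimited statement. For this mechanism the direction is clear: D1 looks better and the D2 minus D1 difference looks smaller. The size is unknown because the protocol states neither the Stage 2 share nor how far the panel relies on baseline tests. The figures of 7.9 and 13.1 points at a 5% share, and 6.9 and 12.3 at 10%, illustrate assumed values at a middle correlation and are not estimates for this trial. If few patients reach Stage 2, the effect is small. Confidence is high for the mechanism and low for any particular magnitude; the net bias of the trial is left open.

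**What to change.** 1. Reword section 10.5.3 so that the incorporation-bias statement covers PET/CT and Stage 1 decisions only, and say that Stage 2 decisions draw on the baseline investigations.
2. Record on the D4 form, separately for diagnosis and for stage, whether D4 was fixed at Stage 1 or Stage 2 and whether it rests on histology.
3. Report the D1 against D2 results (sensitivity, specificity, McNemar's test) for all patients and for Stage 1 patients only.
4. For staging accuracy, show the same Stage 1-only result beside the full result. Restricting staging to patients staged operatively or pathologically would drop many unresected patients and add a selection problem.
5. State that D4 is locked before the panel receives PET/CT information for the question about appropriateness of management.

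The cost is a reworded sentence, a few tick-boxes and one added analysis. The downside is a smaller and more selected denominator in the Stage 1-only analysis. If 10% of 500 patients were settled at Stage 2 and prevalence were unchanged, 450 would remain, about 212 of them diseased (0.47 × 450) instead of 235. Patients left unresolved at Stage 1 are also unlikely to resemble the rest, so the restricted result belongs beside the full one and should not replace it.

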11.1. Screening PET/CT Core Laboratory

A Core Pet/CT Laboratory Facility has been set up as part of the NCRI PET Research Network, Clinical Trials Network at the PET Imaging centre at St. Thomas's Hospital, London. Their role will cover the following:

- Co-ordination of imaging studies in liaison with clinical trials units
- Data transfer, QC and collation processes
- Ongoing QC, Audit and approval of PET Centres
- Specify patient confidentiality, data transfer and related issues.
- To provide advice and guidance to all study centres throughout the study.
- Advice on protocols for PET/CT acquisition and processing

11.2. Processes for PET/CT scanning

Given that PET/CT scanning is a relatively new technology in the NHS, national standardised protocols and quality assurance procedures are actively under development. This national study aims to be widely applicable to many centres and will involve the use of both fixed and mobile scanners following a strict quality assurance programme.

Prior to a site being given the green light to begin recruitment accreditation must be granted by the Core Lab. This will be used to evaluate and resolve image transfer and other quality issues to ensure images acquired from participating centres are of comparable quality.

Individual study participant QC reports will be issued by the core lab on PET/CT images

11.3. Data Transfer

PET Centres submitting data should ensure the data is anonymised and in DICOM Part 10 format. The submitted images must include the attenuation corrected PET, non-attenuation corrected PET and the CT.

The recommended method for electronic data transfer from NHS PET Centres is via the NHS Secure File Transfer Service.

All other sites with appropriate internet access should use the NCRI Core Lab FTP server.

Full instructions can be obtained at the following link; http://www.ncri-pet.org.uk/index.php?option=com_content&view=category&layout=blog&id=14&Itemid=7

Data submitted on DICOM CD should be sent to the NCRI Trials Physicist:

[name] PET Imaging Centre [name],

[name]

St Thomas' Hospital

[name]

[contact] [name]

[contact]

Email: [name]

[contact]

11.4. Recommended standardised criteria for reading and reporting PET/CT

All PET/CT scans will be reported locally according to an agreed protocol (Appendix G). The standardised protocol and criteria for performing and reading of PET/CT scans will be provided to all participating PET/CT centres by the LCTU. PET/CT scans must be reported using manual visual analysis technique, sufficient for the results to be recorded on the PET/CT CRF. In addition it is requested that the Standard

Uptake Values (SUVs) of the scans should also be assessed and reported, to enable the results to be recorded in the PET/CT CRF.

11.5. PET/CT Central Reporting

A central PET/CT reporting facility has been established at the Paul Strickland Scanner Centre at Mount Vernon Hospital, in addition to the designated Core Lab, to provide central PET/CT reports independent of the local hospital, reviewed by two experts in clinical PET/CT and to perform second stage quality assurance on all PET/CT scans. Data will be transferred from the Core lab to the Central reporting facility. Central clinical reports will be produced independently by two designated radiologists expert in PET/CT. If there are any significant differences in the local and central reports the local and central laboratory radiologists will confer and agree on a final report and the principal investigator will be informed. To ensure a full report can be produced the central reporting facility must be in receipt of the following;

- PET/CT Report
- Clinical Details
- PET/CT Request
- CT scan from MDT meeting

Contacts at the central reporting facility;

[name] [name] (Clinical Queries)

Paul Strickland Scanner Centre,
Mount Vernon Hospital,
[name].
[contact]
[contact]
[contact]
Email: [contact]

[name] (QA Queries)

Paul Strickland Scanner Centre
Mount Vernon Hospital
[name].
[contact]
[contact]
[contact]
Email: [contact]

11.6. PET/CT Protocol

Please see Appendix G

12. Statistical Considerations

12.1. Outcome measures

Primary:

1. To determine the incremental diagnostic accuracy and impact of PET/CT in addition to standard diagnostic workup in patients with suspected pancreatic cancer.

Secondary:

1. To evaluate changes in diagnosis, staging, and associated intended patient management through the addition of PET/CT
2. To determine cost effectiveness of the addition of PET/CT in the diagnosis, staging and management of pancreatic cancer.
3. To evaluate the impact of the addition of PET/CT in differentiating pancreatic malignancy from chronic pancreatitis.
4. To identify which groups of patients would most benefit from PET/CT.
5. To report the incremental diagnostic value of PET/CT for particular types of pancreatic tumour.
6. Data will be analysed in separate cohort groups; the subgroups will be as follows (identified through baseline assessment and D1 data):
 - a) No mass on CT
 - b) Chronic pancreatitis
 - c) Resected tumours with no recurrence on CT
 - d) Raised tumour markers but no mass on CT
 - e) Dilated pancreatic duct on CT but no mass on CT

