10.1.1. Diagnosis

Diagnosis will be categorised by the following options:

1. Pancreatic ductal adenocarcinoma
2. Peri-ampullary cancer
3. Cholangiocarcinoma
4. Benign cystic neoplasm
5. Malignant cystic neoplasm
6. Pancreatic pseudocyst
7. Chronic pancreatitis
8. Autoimmune pancreatitis
9. Acute pancreatitis
10. Neuroendocrine tumour
11. Lymphoma
12. Metastasis from non pancreatic primary neoplasm
13. Recurrent pancreatic cancer post resection
14. Normal pancreas
15. Other

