12.4. Statistical Analysis Plan

The analysis will focus on investigating incremental diagnostic accuracy and incremental diagnostic impact. Diagnostic accuracy will be investigated by comparing the baseline diagnosis (D1), and the results of the PET/CT scan with the reference diagnosis (D4); diagnostic impact by comparing the baseline (D1) and post PET/CT (D2) diagnoses with the reference diagnosis (D4).

The diagnostic impact of standard work-up will be estimated by comparing diagnostic decisions made at D1 with the reference diagnosis made at D4 for each of the target conditions (pancreatic malignancy, chronic pancreatitis and the tumour types) and expressed as sensitivities and specificities together with 95% confidence intervals (computed using binomial exact methods). To evaluate the accuracy of staging by standard work-up the analysis will be restricted to individuals with pancreatic malignancy diagnosed at the reference diagnosis. The accuracy of the revised diagnoses made after PET/CT will be assessed in the same way making comparisons between diagnostic and staging decisions made at D2 with the final reference diagnosis.

The initial analysis of the incremental benefit of PET/CT over standard work-up will be assessed through comparing the sensitivity and specificity of diagnostic decisions D1 and D2, in both absolute and relative terms. Tabulations will be created of cross-classifications of the D1 and D2 diagnoses for diseased and non-diseased to investigate the within patient changes induced by the PET/CT scan and their significance assessed using McNemar's test for paired data. This change will be computed for each of pancreatic malignancy, chronic pancreatitis, and the tumour types. Subgroup analyses using GEE regression modelling (taking account of paired data) will be undertaken to investigate whether test performance varies according to presenting conditions.

The incremental accuracy of PET/CT over standard workup will be investigated using regression modelling following the Knottnerus approach summarised by Chan et al. This allows the modelling of a sequence of tests through creative construction of indicator variables, which takes into account the non-independence of test results, but does not alter the value of previous test results when subsequent tests are added to the model. It also allows expression of the incremental diagnostic value as likelihood ratios.

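### Section 12.1 lets the chronic pancreatitis subgroup be taken from the D1 diagnosis; if it is, the D1-versus-D2 accuracy comparison in that group is fixed by selection, and two of the no-mass groups are subsets of a third

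*Protocol*

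**What the plan says.** Section 12.1 adds a subgroup item to the secondary outcome measures: "Data will be analysed in separate cohort groups", and "the subgroups will be as follows (identified through baseline assessment and D1 data". The five groups are (a) no mass on CT, then "b) Chronic pancreatitis", "c) Resected tumours with no recurrence on CT", "d) Raised tumour markers but no mass on CT", and (e) "Dilated pancreatic duct on CT but no mass on CT". No rule is given for recognising group (b).

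Section 10.1.1 lists fifteen D1 diagnosis options; the seventh is "Chronic pancreatitis". Section 10.2 keeps the same categories for D2.

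Section 12.4 measures standard work-up as the D1 decision against the reference diagnosis D4, and the increment from PET/CT as D1 against D2, with McNemar's test. On subgroups it states: "Subgroup analyses using GEE regression modelling (taking account of paired data) will be undertaken to investigate whether test performance varies according to presenting conditions".

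**The concern.** The D1 decision is the comparator in the accuracy analysis. A subgroup formed from that decision is selected on the comparator's result. In a group of patients whom D1 called chronic pancreatitis, every cancer is a D1 miss and every non-cancer a D1 success before any PET/CT information enters. A change at D2 can then go one way only in each disease class.

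Secondary objective 3 asks how PET/CT helps to separate malignancy from chronic pancreatitis, and objective 4 asks who benefits most. An analysis selected in this way would show PET/CT gaining sensitivity and losing specificity in chronic pancreatitis even if D2 labels were reassigned at random.

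A smaller concern is that (a), (d) and (e) are presented as separate groups although they share patients, so agreement between them could be read as independent confirmation.

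**Working it through.** The protocol gives no figure for the subgroups, so the check is on the definitions, with an illustration based on its planning values.

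**Where group (b) can come from.** Baseline assessment includes a general review of medical history (section 9.3). The D1 form also holds CT features: number, size and morphology of lesions, duct dilation, vascular involvement and extra-pancreatic disease (section 8.1). Neither list names chronic pancreatitis. Among the baseline and D1 items the protocol describes, only the D1 diagnosis list does.

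**Inputs.** From section 12.2: D1 sensitivity 81% and specificity 66%; D2 90% and 80%. True changes are therefore +9 and +14 points. Assumptions for illustration: half of D1-negative patients are labelled chronic pancreatitis; a history of it is present in 5% of cancers and 20% of non-cancers; both are unrelated to the other decisions given disease status.

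**Rule 1, D1 diagnosis.** All members are D1-negative, so D1 sensitivity is 0% and specificity 100%. No assumption about size is needed, only one diagnosis per patient and pancreatic cancer as the target. With chronic pancreatitis as the target the result is the mirror image, 100% and 0%.

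**Rule 2, history or D1 diagnosis.**
- Cancers entering as D1-positive: 0.81 × 0.05 = 0.0405. As D1-negative: 0.19 × (1 − 0.5 × 0.95) = 0.19 × 0.525 = 0.09975. D1 sensitivity = 0.0405 / 0.14025 = 28.9%.
- Non-cancers entering as D1-negative: 0.66 × (1 − 0.5 × 0.80) = 0.66 × 0.60 = 0.396. As D1-positive: 0.34 × 0.20 = 0.068. D1 specificity = 0.396 / 0.464 = 85.3%.

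**Rule 3, history only.** Under the same assumptions D1 keeps 81% and 66%, and discordance runs both ways: in cancers 0.19 × 0.90 = 17.1% gained and 0.81 × 0.10 = 8.1% lost.

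**Apparent change from D1 to D2**, first with D1 and D2 independent given disease:

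| Rule for (b) | Sensitivity | Specificity |
|---|---|---|
| D1 diagnosis | 0% to 90% (+90) | 100% to 80% (−20) |
| History or D1 diagnosis | 28.9% to 90% (+61.1) | 85.3% to 80% (−5.3) |
| History only | 81% to 90% (+9) | 66% to 80% (+14) |

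Independence is only one case. Let the proportion positive at both D1 and D2 be j, from 0.71 to 0.81 in cancers and from 0 to 0.20 in non-cancers, which are the limits the four accuracies allow.
- Rule 1: sensitivity change (0.90 − j)/0.19, from +100 to +47.4 points; specificity change −(0.20 − j)/0.66, from −30.3 to 0.
- Rule 2: sensitivity change (0.432 − 0.475j)/0.14025, from +67.6 to +33.7; specificity change (−0.052 + 0.4j)/0.464, from −11.2 to +6.0.

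Across the whole range, both rules overstate the sensitivity gain (true +9) and understate the specificity gain (true +14).

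**Significance under rule 1.** If a paired test were applied in this group, m discordant pairs all in one direction give an exact two-sided McNemar p of 2 × 0.5^m: 0.031 for m = 6 and 0.0078 for m = 8. These counts are illustrative.

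**Nesting.** Every patient in (d) or (e) has no mass, so is also in (a):

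| No mass, with | (a) | (d) | (e) |
|---|---|---|---|
| neither feature | yes | no | no |
| raised marker only | yes | yes | no |
| dilated duct only | yes | no | yes |
| both | yes | yes | yes |

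Patients with a mass are in none of the three. Group (c) may overlap (a), but its wording does not nest it.

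**The case against.** A reader might infer that the plan already makes D1 accuracy 0% and 100% in group (b). The text does not support that. Section 12.1 names baseline assessment as well as D1 data, baseline assessment includes history, and D1 data include CT features. Section 12.4 speaks of presenting conditions. Section 4.5 lists chronic pancreatitis among the hard-to-diagnose patient types and mentions cancer arising in patients who have it, which suggests a background condition and not the MDT's verdict. This stands: the 0%/100% result is conditional.

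It can also be said that mapping a subgroup label to form fields belongs in the statistical analysis plan. That holds for pure detail. Here, though, the protocol itself names D1 data as a source, and using the D1 diagnosis, alone or with history, biases the planned comparison.

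A further stronger reading is that the subgroup model must fail or that objectives 3 to 5 rest wholly on these groups. Section 12.4 assigns subgroups to GEE without naming a link function or interaction term, and does not expressly plan McNemar tests within them. A logistic model with a test-by-subgroup term would have no finite estimate where D1 has no successes, but that model is not stated. Section 12.4 also analyses chronic pancreatitis and the tumour types as target conditions in the whole cohort, so objectives 3 and 5 have a route that this selection does not touch.

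On nesting, separate may only mean reported one at a time, and overlapping descriptive subgroups are common. That makes the point minor, but the subset relation is certain.

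**Conclusion.** The point holds as a conditional one. If group (b) is taken from a single-choice D1 diagnosis and the target is pancreatic cancer, D1 sensitivity of 0% and specificity of 100% follow exactly, and the direction of any D2 change is fixed in advance. The single-choice assumption is supported but not stated: section 10.1.3 allows one or more management options, and section 10.1.1 has no such wording for diagnosis. A mixed rule is less extreme but still biased; its size (about 29% and 85%) depends on the assumed labelling and history rates.

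A group defined by history need not show 81% and 66%, since clinicians know the history when they decide at D1. Any difference would then be a real property of such patients and not an effect of selecting on the D1 answer.

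Only secondary subgroup results are affected. It should be settled before analysis because the remedy is wording.

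**What to change.** State in section 12.1 that group (b) is defined from information independent of the D1 diagnosis category, such as chronic pancreatitis in the medical history recorded at baseline (section 9.3). That makes it a presenting condition, as section 12.4 intends. If patients with a D1 diagnosis of chronic pancreatitis are also of interest, report them as counts reclassified at D2 against D4, without a D1-versus-D2 comparison of sensitivity and specificity.

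Replace the description of the groups as separate with a statement that (d) and (e) are overlapping subsets of (a), so that their results are not read as independent evidence. Splitting (a) into four exclusive groups is optional and would shrink the cells.

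The cost is a change of wording and a smaller group (b), because cases first recognised at D1 are left out. The forms are not shown, so it should be confirmed that the history form captures chronic pancreatitis in usable form.
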